2.3 Investigation Type

Post-market, international, multi-center, prospective, single arm observational registry.

SJM-CIP-10032 Ver. B

ABLATOR Study

October 20, 2015

This observational registry will be conducted in approximately 100 centers worldwide.

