3.1 Registry Flow Chart

Figure 2: Flow Chart

All procedures will follow site standard of care at the site.

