3.2 Case Report Forms Content

Table 1: Data Collection

CRFs \ Visit	Enrollment & Baseline	Ablation Procedure	6 and 12 Months
Enrollment: Informed Consent Process	X		
Baseline: Demographics, Cardiovascular History, AF History, Medical History	X		
Ablation procedure		X	
Device user experience		X	
Follow Up Log*			X
Repeat procedure			(X)
Cardiovascular Serious Adverse Event	(X)	(X)	(X)
Withdrawal	(X)	(X)	(X)
Death	(X)	(X)	(X)

(X) if applicable

* Telephone or office visit

Enrollment & Informed Consent Process

The investigator is responsible for screening subjects for this registry and for obtaining patient informed consent, as applicable per local regulations. Provision of the Informed Consent is mandatory. Informed Consent is required from all patients (or their legal representatives) prior to participation in the investigation. The process of obtaining Informed consent shall comply with the most recent version of the declaration of Helsinki, ISO 14155 and all applicable regulations. The principal investigator or his/her authorized designee will conduct the Informed Consent Process. This process will include a verbal discussion with the patient on all aspects of the clinical investigation that are relevant to the patient's decision to participate in the clinical investigation. It is crucial that this discussion is documented in the source documents (read hospital records of the patient).

The patient will be provided with the informed consent form that is written in a language that is understandable to the patient and has been approved by Ethics Committee. The patient is given ample time to consider participation and ask questions if necessary.

In order to avoid any possible coercion or undue improper influence on, or inducement of the patient to participate, the Sponsor requests the investigator to only sign the informed consent form once the patient has signed and dated the document and therefore decided to participate in the investigation.

Informed Consent of a patient shall always be indicated by personally dated signature of the patient and by the investigator responsible for conducting the informed consent process. It is crucial that the signature of the informed consent is documented in the source documents (read hospital records of the patient).

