One original signed consent document must be retained on file by the investigator and a second original signed consent document is provided to the subject (investigator's responsibility). The patient's legal rights will not be waived nor the appearance that these will be waived. Native non-technical language, understandable for the patient, will be used. Important new information that becomes available throughout the Registry will have to be provided in writing to new and existing patients. If relevant, all affected patients shall be asked to confirm their continuing informed consent in writing.

Baseline Visit

The following baseline information will be collected;

- Patient demographics
- Atrial fibrillation History (such as type, frequency, duration of atrial fibrillation and other arrhythmias other than AF),
- Cardiovascular history (NYHA class, LA diameter, LV EF% and degree of valvular heart disease),
- Cardiac medical history (pre-existing cardiac conditions and cardiac procedures).

Ablation procedure

- Devices used
- Ablation parameters
- Ablation success definition and result
- Operator feedback (Device combination chosen, device maneuverability, ease of use in combination with other device)
- Number, experience and type of attending personnel
- Definition of standard of care (follow-up procedures and occurrence)

6 and 12 Month Follow-up (+/- 30 days)

- Recurrence of atrial arrhythmias: list of atrial arrhythmias since last visit, classify episodes, duration of the episodes, (only events with source data evidence are to be recorded).
- Changes in therapy (new antiarrhythmic drug, redo procedures).
- In case of Repeat Ablation Procedures, reconnections and new ablations will be recorded.

Cardiovascular Serious Adverse Event

An adverse event is reportable in this registry when the event is deemed of cardiovascular origin and has the potential of leading to:

- Death
- A serious deterioration in the health of the subject, that can either result in:
 - o A life-threatening illness or injury OR
 - o A permanent impairment to a body structure or a body function OR
 - o An in-patient or prolonged hospitalization OR
 - o A medical or surgical intervention to prevent life-threatening illness or injury or permanent impairment to a body structure or a body function OR
 - o A malignant tumor
- Fetal distress, fetal death or a congenital abnormality or birth defect

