4.3 Monitoring

Centralized monitoring will occur through routine internal data review. This monitoring is designed to identify missing and inconsistent data, data outliers, and potential protocol deviations that may be indicative of site non-compliance. On site monitoring may occur at the discretion of the sponsor.

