4.5 Statement of Compliance

The registry will be performed in accordance with the most current versions of the World Medical Association (WMA) Declaration of Helsinki, ISO 14155 and any regional and/or national regulations and will be compliant to this International Standard and any regional and national regulations, as appropriate.

The investigator shall not start enrolling patients or requesting informed consent from any patient prior to obtaining Ethics Committee approval and Competent Authority approval, if applicable, and authorization from the sponsor in writing.

In case additional requirements will be imposed by the Ethics Committee or Competent Authority they shall be followed, if appropriate.

5 Risks and Benefits of the clinical investigation

This registry will follow site standard practice procedures, therefore there are no risks or benefits associated with participating in this registry for the patient. A long term benefit for therapy delivery is expected based on the scientific outcome of the registry data analysis.

6 Statistical considerations

This is a post-market, international, multi-center, single arm observational registry. The objectives of this Registry are as follows:

- To confirm patient safety as part of the post market surveillance study.
- To assess performance of a combination of SJM products during procedures
- To assess the learning curve with a combination of SJM products.
- To collect operator feedback on a combination of SJM products
- To compare the acute and long-term effectiveness according to technique used.
- To analyze procedure efficiency according to technique used.

Up to 2,000 patients will be enrolled in this registry, which is expected to be adequate to address the objectives of this registry. Descriptive statistics will be used to summarize baseline and demographic data, procedural information, adverse events and recurrence of atrial arrhythmias. Continuous variables may be summarized using either mean, standard deviation and range, or median and interquartile range as applicable. Categorical variables will be summarized as frequencies and proportions. Kaplan-Meier time to event analysis may be used to summarize recurrent atrial arrhythmias. To assess learning curve, appropriate statistical analysis will be used to assess the influence of physician experience on procedural outcomes or adverse events.

7 Data Management

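### The listed follow-up items record arrhythmias with source evidence but not whether a patient's rhythm was checked, so recurrence by technique cannot be fully separated from monitoring

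*Combined protocol and SAP*

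**What the plan says.** Section 3.2 lists three items for the 6- and 12-month follow-up:

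- recurrence, as a "list of atrial arrhythmias since last visit" with classification and duration of episodes, restricted so that "only events with source data evidence are to be recorded";
- changes in therapy (new antiarrhythmic drug, redo procedure);
- findings at a repeat ablation.

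In Table 1 the Follow Up Log is required at both time points, and its footnote allows "Telephone or office visit". Section 3.1 says "All procedures will follow site standard of care at the site", and section 2.3 says "This observational registry will be conducted in approximately 100 centers worldwide".

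One item does concern monitoring. It is listed under the ablation procedure: "Definition of standard of care (follow-up procedures and occurrence".

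Sections 2.2 and 6 both name a comparison of long-term effectiveness by technique as an objective. For the analysis, section 6 plans descriptive statistics and adds that "Kaplan-Meier time to event analysis may be used to summarize recurrent atrial arrhythmias". It gives no censoring rule, no rule for patients without a rhythm recording, and no adjustment for monitoring.

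**The concern.** Requiring source evidence for a recurrence is sound. The gap is on the other side of the ledger: the listed items leave no trace of a check that was done and negative, or of no check at all. A patient with several clean recordings and a patient reached only by telephone can both have a complete follow-up with an empty arrhythmia list.

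Recurrence is the listed follow-up outcome that bears most directly on long-term effectiveness. If empty lists are counted as event-free, recurrence may be too low by an unknown amount. If the share of unmonitored patients differs between techniques, for example because sites differ in both, part of an apparent technique difference is a monitoring difference. Per-patient monitoring that was not collected during follow-up cannot easily be recovered at analysis.

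**Working it through.** **1. What the items can and cannot distinguish.**

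| Situation at 6 or 12 months | What the listed items show |
|---|---|
| Visit missed | No Follow Up Log |
| Patient withdrawn or died | Separate form |
| Recurrence with source evidence | Arrhythmia entry |
| Rhythm checked, no recurrence | Empty list |
| Follow-up done, rhythm not checked | Empty list |

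Only the last two rows are confused. Central review (section 4.3) does not resolve them. "This monitoring is designed to identify missing and inconsistent data", but an empty arrhythmia list is a valid entry. The site's follow-up standard shows what was planned, not what each patient had.

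**2. No plan figure to reproduce.** Section 6 states up to 2,000 patients without a derivation. No recurrence rate, group size, test or significance level is given.

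**3. Illustration; every input is an assumption.**

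- R = true recurrence, the same with both techniques: 30% (range 20-40%).
- m = share with completed follow-up but no monitoring: 10% vs 20%.
- s = share of unmonitored recurrences that surface anyway: 0 or 0.5.
- Empty lists are counted as event-free.

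Recorded recurrence = R × (1 − m + m·s).

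- s = 0: 0.30 × 0.90 = 27.0% vs 0.30 × 0.80 = 24.0%.
- s = 0.5: 0.30 × 0.95 = 28.5% vs 0.30 × 0.90 = 27.0%.

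The false difference is thus 3.0 or 1.5 points. It sits in the estimate, whether or not a test is run.

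**4. Chance of a false difference under a nominal test.** Two-proportion z-test, pooled variance, two-sided 5%. With SE0 the pooled and SE1 the unpooled standard error, the chance is Φ((d − 1.96·SE0)/SE1) plus the opposite tail.

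For 27% vs 24% with 1,000 per group:

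- SE0 = √(2 × 0.255 × 0.745/1,000) = 0.01949
- SE1 = √((0.27 × 0.73 + 0.24 × 0.76)/1,000) = 0.01948
- (0.03 − 0.0382)/0.01948 = −0.42, so the chance is 0.34.

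| 10% vs 20% unmonitored, R = 30% (range over R = 20-40%) | 250 per group | 500 per group | 1,000 per group |
|---|---|---|---|
| none surface | 0.12 (0.09-0.16) | 0.19 (0.13-0.27) | 0.34 (0.22-0.47) |
| half surface | 0.07 (0.06-0.08) | 0.08 (0.07-0.10) | 0.12 (0.09-0.15) |

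With 10% vs 15% unmonitored, half surfacing and 500 per group, it is 0.055-0.062. With equal shares it is 0.05.

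**5. Which definition of 'assessed' helps.** Suppose any recording, including a symptom-driven one, counts as assessed. Unmonitored patients whose recurrence surfaces then re-enter the denominator as events only:

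rate = R(1 − m + m·s) / (1 − m + m·R·s).

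At R = 30%, s = 0.5, this gives 0.285/0.915 = 31.1% vs 0.270/0.830 = 32.5%. The bias is reversed. With 1,000 enrolled per group the false-difference chance is 0.085-0.101 over R = 20-40%, against 0.089-0.153 with no fix, which is little gain. Limiting the estimate to patients with scheduled monitoring gives 30% vs 30% and a chance of 0.05, provided that being unmonitored is unrelated to recurrence.

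**The case against.** **The form is not shown.** Section 3.2 summarises content; the Follow Up Log itself is not in the documents, and section 9 treats case report forms as separate documents. Appendix A foresees worksheets for required data not routinely collected. This stands: the absence can be asserted only for the listed items. Even a fuller log would leave section 6 without a rule for unassessed patients.

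**Other routes bring recurrences to light.** Arrhythmia, palpitation and worsening of pre-existing atrial fibrillation are named among the potential cardiovascular serious adverse events, reportable from enrollment to the end of the registry. New antiarrhythmic drugs and redo procedures are also recorded. This stands, and makes the none-surfacing rows an extreme. The safety route covers serious episodes only.

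**No test is planned, and large groups are unlikely.** Both stand. Two groups of 1,000 need exactly two techniques at the enrolment cap, while section 1 names several ablation approaches and section 2.5 allows many device combinations. The bias in the estimate remains, and comparison is the protocol's own objective.

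**Uneven detection belongs to any standard-of-care registry.** True, and a log will not find missed recurrences. It will show where nobody looked.

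**Stronger readings that the documents do not support.**

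- A reader might infer that the plan counts unmonitored patients as event-free. That is a likely default but is written nowhere.
- A reader might infer that monitoring and technique cannot be separated at all. The site follow-up standard is collected, so part of the difference can be adjusted for.
- A reader might infer from the regional device lists in section 2.5 that technique and region coincide. The overlap is partial: TactiCath is in two of the three lists, and the sheath, diagnostic catheters and mapping system are the same in all. Only FlexAbility and the CoolFlex family appear in one list each.

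**Conclusion.** The concern holds in a limited form. Among patients with a completed follow-up, the listed items cannot tell a negative rhythm check from no check, and section 6 does not say how such patients enter the recurrence analysis. A technique difference in recurrence therefore cannot be fully separated from a monitoring difference.

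The size is unknown from the documents. On the assumptions above, the false difference at a true recurrence of 30% is 1.5 to 3 points. The chance of nominal significance runs from close to the 5% level in small groups with half surfacing to about one in three at 1,000 per group with none surfacing. This rests on empty lists being counted as event-free and on monitoring that differs by technique. A reader might infer that a particular technique is favoured; nothing in the documents gives a direction, and equal monitoring gives no bias between techniques.

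Confidence is high on what the listed items and section 6 omit, and medium on the consequence because the log is not shown. The change is a cheap improvement to a stated comparative objective; the point does not call the whole registry into question.

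**What to change.** 1. If the Follow Up Log does not already hold it, add a short entry at 6 and 12 months: whether any rhythm recording was done under site care since the last visit (yes/none), its type, the date of the last one, and whether any was scheduled rather than symptom-driven. Negative results count.
2. State in section 6 that patients with no scheduled recording are reported, by technique, as 'not systematically assessed'. Give the recurrence estimate for all patients and for those with scheduled monitoring. Do not define 'assessed' as any recording, because symptom-driven recordings reverse the bias.
3. Stratify or adjust the technique comparison by the site follow-up standard already collected at the procedure. Say that it is a proxy that reduces the bias but may not remove it. Where a technique occurs under only one standard, report it descriptively.

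Cost: a few log fields and some wording in section 6; no tests or visits are added. There is a little more data entry, some negative checks will be hard to obtain by telephone, and the recurrence-free figure may look less favourable. The scheduled-monitoring estimate is unbiased only if being monitored is unrelated to recurrence, so both estimates should be shown.

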A planned hospitalization for a pre-existing condition is not considered a serious adverse event.

Potential Cardiovascular Serious Adverse Events (SAEs) include but are not limited to the following:

Abnormal ECG, Angina (chest pain), Arrhythmia, AV fistula, Complete heart block, Coronary artery injury, Cardiac perforation, Cardiac Thromboembolism, CHF exacerbation – fluid overload, Component damage to ICD or implantable pacemaker, Death, Dislodgement of implantable cardioverter defibrillator or permanent pacing lead, Endocarditis, Exacerbation of pre-existing atrial fibrillation, Heart Failure, Hypotension, Inadvertent AV block (complete heart block), Left atrial/esophageal fistula, Myocardial infarction, Obstruction/perforation/damage of the vascular system, Palpitation, Pericardial effusion/cardiac tamponade, Pericardial effusion without tamponade, Pericarditis, Pulmonary vein dissection, Pulmonary vein stenosis, Pulmonary vein thrombus, Temporary or complete heart block, Unintended (in)complete AV, sinus node, heart block/damage, Vessel wall/valvular damage or insufficiency and Ventricular arrhythmia requiring defibrillation.

Procedure for assessing, recording and reporting SAEs:

Cardiovascular SAEs must be reported following local regulation, no later than 7 days from site being made aware of the event. All cardiovascular SAEs between patient enrollment and end of registry must be reported to the sponsor and to the local ethics committees, as per local regulations.

Should an SAE occur, complete and submit an Adverse Event form to St. Jude Medical.

Additional information can be requested, if necessary, by the Sponsor for reporting of SAEs to regulatory authorities. The investigator must notify the Ethics Committee, if appropriate, in accordance with national and local laws and regulations.

Death

All patient deaths that occur during this registry must be reported to SJM within 72 hours of the center becoming aware of the death. An Adverse Event form should be completed for all deaths at all sites.

Protocol Deviations

Investigators are required to adhere to the study protocol, signed Investigator's Agreement, applicable federal (national) or state/local, laws and regulations, and any conditions required by the Ethics Committee or applicable regulatory authorities. A protocol deviation is used to describe situations in which the study protocol was not followed. All deviations from the study protocol must be reported to SJM.

Withdrawals

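### Mandatory event reporting is tied to cardiovascular SAEs plus deaths, so non-fatal procedure- or device-related SAEs deemed non-cardiovascular have no clear required route into the safety data

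*Combined protocol and SAP*

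**What the plan says.** All event-reporting text is in Section 3.2 of the combined protocol and SAP.

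- **Reportability rule:** "An adverse event is reportable in this registry when the event is deemed of cardiovascular origin and has the potential of leading to" death, serious deterioration in health, or fetal harm.
- **Form:** the serious-event row of Table 1 is labelled "Cardiovascular Serious Adverse Event". Death has its own row. There is no row for SAEs in general.
- **Deadline:** "Cardiovascular SAEs must be reported following local regulation, no later than 7 days from site being made aware of the event".
- **Duty to report:** "All cardiovascular SAEs between patient enrollment and end of registry must be reported to the sponsor", and also to the local ethics committees.
- **Examples:** the list opens with "Potential Cardiovascular Serious Adverse Events (SAEs) include but are not limited to the following". It is open-ended, but it is a list of cardiovascular SAEs.
- **Death:** "An Adverse Event form should be completed for all deaths at all sites", so deaths of any cause are covered.
- **Unqualified wording:** "Should an SAE occur, complete and submit an Adverse Event form" and "by the Sponsor for reporting of SAEs to regulatory authorities" do not contain the word cardiovascular.

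The first objective, in Section 2.2 and again in Section 6, is to confirm patient safety under post-market surveillance, without restriction to cardiovascular events. Section 6 plans a descriptive summary of adverse events and defines no subset related to the procedure or a device.

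**The concern.** The rule sorts events by organ system, as deemed by the site, and not by whether the procedure or a device caused them. A nerve injury or a respiratory event after ablation could be serious, non-fatal and clearly procedural. A site that deemed it non-cardiovascular could follow the reportability rule exactly and not report it. The protocol does not say who makes that judgement or by what criterion, so two sites could classify the same event differently.

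What is at stake is how the safety summary is read. Few or no non-cardiovascular procedural harms in the final tables could be taken as evidence of safety when sites were not clearly asked to report them. Section 7 allows the data to be used in support of a market-approval application, so the reading matters beyond the registry.

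**Working it through.** The plan states no safety figure to reproduce, so the main check sets the sections side by side.

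**1. Scope of what is collected against scope of the objective**

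| Place | Scope |
|---|---|
| Section 2.2 and Section 6, first objective | Patient safety, no organ-system limit |
| Section 3.2, reportability rule | Cardiovascular origin and a seriousness criterion |
| Section 3.2, 7-day deadline | Cardiovascular SAEs |
| Section 3.2, duty to report to sponsor and ethics committees | Cardiovascular SAEs |
| Section 3.2, Table 1 | Cardiovascular SAE form; Death form |
| Section 3.2, Death | All causes |

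What is left over is the non-fatal SAE that a site deems non-cardiovascular, including one related to the procedure or a device.

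**2. Does another listed item collect it?** The ablation-procedure items in Section 3.2 are devices, ablation parameters, success, operator feedback, personnel and standard of care. The follow-up items are arrhythmia recurrence, changes in therapy and repeat ablation. Neither list asks for complications. Central monitoring (Section 4.3) looks for missing or inconsistent data, outliers and deviations, and on-site visits are at the sponsor's discretion. Neither is described as a search for events outside the reporting rule.

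**3. Does the unqualified wording supply a route?** In "Potential Cardiovascular Serious Adverse Events (SAEs) include but are not limited to the following" the abbreviation SAEs is introduced inside the term for cardiovascular events. "Should an SAE occur, complete and submit an Adverse Event form" follows under the same topic and carries no deadline of its own. It can be read as covering every SAE or only cardiovascular ones. Section 4.5 commits the registry to ISO 14155 and to national rules, but names no registry form or field for other SAEs. The scope is therefore ambiguous, and no required route is set.

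**4. Illustration only: what an absence of reports would mean.** The plan sets no safety threshold and the documents give no capture share. These numbers show the general effect of incomplete reporting and do not size this gap. With zero events in N patients and full capture, the one-sided 95% upper bound on the rate is 1 − 0.05^(1/N).

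- N = 2,000 (the maximum enrollment): 1 − 0.05^(1/2000) = 0.001497, or 0.15%.
- N = 1,000 (assumed): 0.002991, or 0.30%.

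If only a share c of such events reaches the data, the bound on the true rate is the full-capture bound divided by c. For N = 2,000:

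- c = 0.50: 0.1497% / 0.50 = 0.30%.
- c = 0.25: 0.1497% / 0.25 = 0.60%.
- c = 0.10: 0.1497% / 0.10 = 1.5%.

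With no capture there is no bound.

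**5. Reporting burden of the wider rule**, at an assumed rate of 0.1% to 1.0% for the added events (not in the documents): 2,000 × 0.001 = 2 and 2,000 × 0.01 = 20 extra reports. Over about 100 centres (Section 2.3), the upper figure averages 20/100 = 0.2 per centre. That is a mean, and a single centre could have more.

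**The case against.** The strongest defence is that this is a deliberate and consistent scope choice. It is a single-arm post-market registry of commercially available devices under site standard of care, and the cardiovascular limit is applied the same way in Table 1, the reportability rule and the reporting procedure. The example list already names the main serious cardiac and vascular harms and includes left atrial/esophageal fistula, which crosses organ systems. The threshold is broad, since potential for a serious outcome is enough. This stands: the gap is confined to non-fatal events deemed non-cardiovascular. It does not answer the mismatch, because the objective is not limited in the same way.

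A second objection concerns Section 4.4. A reader might infer that its termination ground, an unanticipated device-related SAE that cannot be prevented in future cases, directly contradicts the reporting rule. The documents do not support that. SAE is open to the same two readings there as in Section 3.2, the ground is one example in a non-exhaustive list, and nothing says registry data must trigger it. It is supporting context only; the contrast with the first objective carries the point.

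A third objection is that the numbers rest on assumptions. That also stands. The documents give no event rate or capture share, and the planned safety summary is descriptive. The point therefore rests on the text.

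**Conclusion.** The concern holds as a mismatch between the reporting rule in Section 3.2 and the unrestricted safety objective in Sections 2.2 and 6. Followed as written, the plan can under-ascertain non-fatal procedure- or device-related harm that a site deems non-cardiovascular. It should be corrected, and the correction is cheap.

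The size of the gap cannot be derived from the documents. The reading of the text needs no assumption; the bounds and the burden figures do, and they are illustrative.

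Two stronger conclusions are tempting. A reader might infer that such events have no route at all, or that they will be lost. The unqualified SAE sentence, the mention of reporting to regulatory authorities and the ISO 14155 clause leave room for a site to report them, so the supportable claim is that no clear required route exists. A reader might also infer that relatedness is not recorded. The Adverse Event form is not among the documents, so that cannot be asserted.

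**What to change.** 1. Amend the reportability sentence in Section 3.2 to cover all cardiovascular SAEs plus any SAE judged related to the procedure or a study device, whatever the organ system.
2. Align the Table 1 label, the 7-day sentence and the duty-to-report sentence with it, and define SAE once for the whole protocol.
3. Record relatedness to procedure and device, if the Adverse Event form does not already do so.
4. In Section 6, keep the summary of all reported SAEs and add a tabulation of those related to the procedure or a device.
5. If the sponsor keeps the narrower scope, state in the objective and in the report that the safety conclusion covers only cardiovascular SAEs and deaths. The same statement is needed for patients enrolled before any change.

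**Cost.** Steps 1 to 4 are a few lines of text and possibly one form field. They need an amendment with a justification statement, and notification or approval by ethics committees and authorities where required (Section 9), across about 100 centres. The added reporting is small under the assumed rate. Relatedness is a site judgement, which is why the summary of all reported SAEs should stay beside the related subset. If enrollment has begun, ascertainment will differ before and after the change, and the report must say so. Step 5 alone changes no data collection and would prevent the misreading, but it would leave these harms without a clear required route.
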